2.1. Primary outcome and endpoints

To determine the rate of transient and permanent hypocalcemia:

- Transient hypoparathyroidism as defined by a Day 1 serum parathyroid hormone (PTH) level of <10 pg/ml
- Post-operative serum calcium (mg/dL) and PTH (pg/ml) at Day 12 and Month 6

- Total calcium consumption in first 2 weeks (total gm)
- Hypocalcemia symptoms in first 2 weeks (average episodes/day)
- Hypocalcemia symptom severity scale (range of 1-5)
- Requirement for calcium and calcitriol at Month 6 (or, if laboratory values at visit reveal calcium < 8 mg/dL and PTH <15 pg/ml)

Calcium and PTH levels, calcium intake, and hypocalcemia symptoms will be monitored post-operatively (at Day 1, Day 12, and Month 6) to examine how parathyroid function is affected by a CND.

Hypoparathyroidism can lead to paresthesias and muscle cramps and is a known complication of total thyroidectomy, requiring frequent treatment with calcium and vitamin D. This risk is increased with a CND and is thus important to quantify when examining the risk/benefit ratio. Because calcium supplementation is routinely administered for symptoms of hypocalcemia in the post-operative period and this may impact the interpretation of laboratory evaluations, we will be evaluating a variety of metrics to assess the incidence and impact of hypocalcemia on patients.

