Eligible patients will have a thyroid nodule >1 cm in size that is consistent with or suspicious for PTC on a pre-operative biopsy. All biopsies will be reviewed by pathology to confirm eligibility. Patients with T4 (tumor of any size that extends beyond the thyroid) tumors, history of degenerative neurological diseases, pre-operative vocal cord paralysis or other vocal cord pathology will be excluded. All patients will undergo a comprehensive neck ultrasound to evaluate for lymphadenopathy by an experienced thyroid radiologist. A comprehensive evaluation of lymph nodes in levels 1-6 will be performed. If the patient is proven to have lymph node involvement they will be ineligible for the randomization arms.

Patients without evidence of nodal involvement on pre-operative imaging will be eligible for the randomization arms of the trial and consented pre-operatively. Per standard of care at our institution and the recommendations of the ATA, thyroid cancer patients are offered various surgical treatments depending on the nature of their disease. For example, for those whose cancer is limited to only one side of the thyroid, a partial lobectomy may be the appropriate treatment. For this reason, we will only approach patients who have elected to undergo total thyroidectomy for the randomization arms. Patients who are eligible for the trial but not for randomization (i.e. have evidence of lymph node disease or are choosing a thyroid lobectomy) will be approached for consent into the standard of care arm.

Pre-Operative Screening and Testing: Pre-operative laboratory testing will include calcium, PTH, and Vitamin D testing (Aim 1), a comprehensive voice and swallow¹ evaluation (Aim 2), and a complete quality of life evaluation using validated questionnaires and semi-structured interviews (Aim 3). Patients eligible for the randomization arms will then be randomly assigned - after intraoperative confirmation of no suspicious adenopathy or gross local invasion - to one of two treatments on the day of surgery; Arm 1: total thyroidectomy alone, or Arm 2: total thyroidectomy with ipsilateral prophylactic CND. Randomization will be stratified by both age and tumor size to allow appropriate comparisons between groups. Allocation schedule will not be known to study staff prior to consenting.

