5.4. Allocation to intervention

Patient allocation will be randomized by using a permuted block randomization stratified by age (\geq or $<$ age 45) as the staging of thyroid cancer is different based on patient age, and tumor size (T1-T2 vs. T3) as the benefit of prophylactic central neck dissection may be greater in patients with T3 tumors. We have no predefined recruitment goal for participants \geq or $<$ age 45. For tumor size we would like to recruit 25% of patients with T3 tumors (size $>$ 4 cm or minimal extrathyroidal extension); this is estimated to be 25% of our eligible population, so we believe that this goal is achievable. Randomization will occur on the day of surgery in the operating room after confirming no suspicious adenopathy and will only be known by the operating surgeon. Participants will be blinded to their treatment allocation until their 2-week follow up appointment at which time their pathology report will be reviewed and they will be told of their treatment allocation.

6. Participant recruitment and consent

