Calcium	Lab	X	X	X		X	Performed only if month 6 value is abnormal
PTH	Lab	X	X	X		X	Performed only if month 6 value is abnormal

Variable	Unit	Pre	Time Points for Data Collection				
			Post-Op Day 1	Post-Op 2 Weeks	Post-Op 6 Weeks	Post-Op 6 Mo	Post-Op 12 Mo
Vitamin D (if PTH is high)	Lab	X					
Neck ultrasound	Imaging	X				X	X
FNA result	Lab	X					
Hypocalcemia symptom log	Rating			X			
TSH & repeat TSH (if needed)	Lab				X	X	X
Radioactive Iodine scan dose and scan results (randomized patients only)	Imaging				X ⁴		If indicated clinically
Unstimulated Tg level	Lab				X	X	X
Stimulated Tg level	Lab				X ⁵		X ⁵

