review of the literature and we purposely chose a number on the lower end of quoted ranges to ensure that we are not underestimating our sample size. With these assumptions the sample size is 116, with 58 patients per arm. Due to the short follow up for our primary endpoint (post-operative day 1) and for our secondary endpoints (<12 months), we anticipate no significant loss to follow up. For our secondary aims, we chose the Dysphonia Severity Index (DSI) as representative and found a prior thyroid surgery study (45) showing that as few as 8 patients in a negative voice outcome group were sufficient to detect clinically meaningful differences on this measure versus patients with normal vocal functioning at 6 months post-op. Thus, the sample size in our study should be adequate to address our secondary aims even if there is attrition/ loss to follow-up.

The number of patients who must be consented will be larger than the final sample size because a portion of patients that are enrolled and evaluated pre-operatively may not be randomized the day of surgery (because malignancy is not proven intraoperatively, suspicious adenopathy is identified, or there is gross local invasion). We aim to increase the sample size by 20% to accommodate for this.

We have found in our examination of preliminary data that our objective measures are not effectively capturing the impact of surgery on patients and that the most critical and meaningful data that we are obtaining from our study is from the in-depth patient interviews. Given the value of our qualitative data, we need to ensure that we are capturing adequate qualitative data to identify differences between the objective and patient-reported evaluations of experiences with hypocalcemia and voice and swallowing problems caused by transient or permanent nerve injury. Ultimately, we plan to make our existing study aims even more robust by incorporating both objective and subjective data into each of our primary and secondary outcomes measures.

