8.2. Analysis of endpoints

For all primary aims, data will be analyzed using a mixed model two-way analysis of variance examining the effects of treatment group, time and factor interactions, such as radioactive iodine dose. Evaluation time periods (pre-surgery, Day 12, Week 6, Month 6, and 1 Year) will serve as between subjects factor and treatment group (prophylactic CND versus no CND) will serve as the between subjects factor. Experiment-wise error will be controlled with an appropriate adjustment to the alpha-level. Prior to each analysis, we will plot all data and carefully examine each analysis to ascertain that the assumptions of ANOVA are not violated. Data will be transformed as necessary to better conform to the assumptions. Nonparametric statistics will be used when assumptions for ANOVA are not achieved. Statistical support for the study design and analysis will be performed by [name] who will perform analyses with SAS statistical software (SAS Institute Inc., Cary, NC).

9. Risks and benefits of trial participation

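### Section 8.2 puts the pre-surgery value inside the outcome time factor, adjusts for no baseline, and does not name the term that tests the CND effect

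*Combined protocol and SAP*

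**What the plan says.** For all primary aims, Section 8.2 specifies that "data will be analyzed using a mixed model two-way analysis of variance examining the effects of treatment group, time and factor interactions". It then lists the time levels: "Evaluation time periods (pre-surgery, Day 12, Week 6, Month 6, and 1 Year) will serve as between subjects factor". It does not say whether the group main effect or a group-by-time term is the test of CND, and no section uses a pre-operative value as a covariate.

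The baseline data exist. Section 3 states "Pre-operative laboratory testing will include calcium, PTH, and Vitamin D testing (Aim 1", and Section 5.4 states "Randomization will occur on the day of surgery in the operating room after confirming no suspicious adenopathy", so these values precede allocation. Section 2.1 lists among the primary measures "Post-operative serum calcium (mg/dL) and PTH (pg/ml) at Day 12 and Month 6". In the Section 7.1 table, calcium and PTH have no Week 6 entry, and the 12-month entry reads "Performed only if month 6 value is abnormal". The routine levels of this model for calcium and PTH are therefore pre-surgery, Day 12 and Month 6. Calcium and PTH are also drawn on Day 1, but Day 1 is not a level of the time factor.

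The endpoint behind the sample size is a different one: "Transient hypoparathyroidism as defined by a Day 1 serum parathyroid hormone (PTH) level of <10 pg/ml". Section 8.1 confirms the timing: "Due to the short follow up for our primary endpoint (post-operative day 1".

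**The concern.** Randomisation makes the expected arm difference at pre-surgery zero (in expectation, not in the sample at hand). A group main effect averaged over all time levels includes that zero, so it understates a real post-operative difference. A group-by-time test avoids the dilution. However, it either spreads the signal over several degrees of freedom or, as a post-minus-pre contrast, carries the variance of a change score. A covariate-adjusted comparison avoids both losses.

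At stake are the size of the reported calcium and PTH differences and the power to detect them, most of all near the reduced minimum of 70 randomised patients in Section 8.1. Because no term is named, the choice could also be made after the data are seen. Correcting the description of time from a between-subjects to a within-subjects factor would cure none of this.

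**Working it through.** **Inputs.** From the documents: the five time levels (8.2); randomisation in the operating room (5.4); calcium and PTH at pre-surgery, Day 12 and Month 6 (3, 2.1, 7.1); 58 per arm, and 35 per arm at the minimum of 70 randomised (8.1); alpha 0.05, sidedness not stated (8.1). Assumed, because the documents give no value: SD scaled to 1, sustained effect d = 0.5, equal correlation r between visits of 0.3, 0.5 or 0.7, a two-sided test and complete data.

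**1. The plan's own figure.** For 12% against 36% with power 0.80:

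n0 = [1.960 × √(2 × 0.24 × 0.76) + 0.842 × √(0.12 × 0.88 + 0.36 × 0.64)]² / 0.24² = 48.5

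With continuity correction, n = (48.5/4) × [1 + √(1 + 4/(48.5 × 0.24))]² = 56.5, so 57 per arm and 114 in total. This is within two patients of the stated 116. It is a two-proportion comparison on Day 1 and does not use the Section 8.2 model.

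**2. Dilution of the main effect.** With T time levels, one of them pre-surgery, a sustained difference d becomes d × (T − 1)/T. That is 2/3 of d for T = 3 (calcium, PTH) and 4/5 of d for T = 5 (quality-of-life scores). This step needs no assumption about SD or correlation.

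**3. Power, three visits.** The variance of an arm difference is (2/n) × V. The one-degree-of-freedom powers use the t distribution. Worked at r = 0.5, n = 58:

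- Main effect: effect 0.333; V = (1 + 2r)/3 = 0.667; SE 0.152; ratio 2.20; power 59%.
- Omnibus interaction: noncentrality n × d² × (T − 1)/[2T(1 − r)] = 58 × 0.25 × 2/3 = 9.67, F on 2 and 228 df; power 80%.
- ANCOVA on the post-operative mean: V = (1 + r)/2 − r² = 0.50; SE 0.131; ratio 3.81; power 97%.
- ANCOVA at one visit: V = 1 − r² = 0.75; SE 0.161; ratio 3.11; power 87%, or 80% at alpha 0.025 (Bonferroni over two visits).

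Power (%) at r = 0.3 / 0.5 / 0.7:

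| Test | 58 per arm | 35 per arm |
|---|---|---|
| Group main effect, pre-surgery included | 68 / 59 / 51 | 47 / 39 / 34 |
| Omnibus group-by-time | 64 / 80 / 96 | 42 / 56 / 79 |
| ANCOVA, post-operative mean | 95 / 97 / 99 | 79 / 83 / 93 |
| ANCOVA, one visit | 80 / 87 / 96 | 58 / 66 / 82 |
| ANCOVA, one visit, Bonferroni over two | 71 / 80 / 93 | 46 / 55 / 74 |

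**4. A one-degree-of-freedom post-minus-pre contrast.** V = (1 + r)/2 + 1 − 2r. At r = 0.5 this is 0.75 against 0.50 for ANCOVA on the mean. The contrast is undiluted but needs 1.5 times the patients for equal power.

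**5. Effect at Day 12 only** (r = 0.5, 58 per arm). The post-operative mean carries 0.25 SD: 0.25/0.131 = 1.90, power 47%. The main effect has 19%. The interaction stays at 80%, because the profiles (0, d, 0) and (0, d, d) have the same sum of squares about their mean, 2d²/3. Day 12 ANCOVA has 87%.

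**The case against.** Several objections stand.

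- A reader might infer that the CND effect is diluted whatever test is used. The documents do not support that. Section 8.2 also names interactions, group-by-time is a natural treatment test in a pre/post design, and it is not diluted. Keeping baseline in the response vector is legitimate and does not bias that term.
- A reader might infer that the trial's main power calculation is undermined. It is not. The powered endpoint is binary PTH on Day 1, which is not a level of this model.
- A reader might take the 97% as the gain from reporting adjusted differences visit by visit. That figure belongs to the post-operative mean. Section 8.2 requires experiment-wise error control, and with Bonferroni over two visits the per-visit comparison roughly equals the omnibus interaction at r = 0.5 (80% against 80%; 55% against 56% at 35 per arm). At r = 0.7 it falls below it (93% against 96%; 74% against 79%).
- A sustained effect may be a poor assumption. Section 8.1 describes transient hypoparathyroidism as much more frequent than permanent. With a Day 12-only effect, the omnibus interaction beats ANCOVA on the post-operative mean.
- The reach is limited. Among the primary measures, only calcium and PTH have both a pre-operative value and repeated follow-up. Calcium consumption, the symptom log and the Month 6 supplement requirement have no baseline to adjust for. The 4/5 figure concerns secondary scores. The clinician-rated voice measures are not routine five-visit outcomes, because Section 7.1 repeats them only after an abnormal examination.

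What the objections do not remove is the gap itself. No term is named, one natural reading is attenuated, and an available baseline goes unused. For the same contrast, in the grid above, adjustment beats the main effect at every correlation. A single pre-named adjusted contrast matches or beats the omnibus test, provided it fits the effect profile.

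**Conclusion.** The point holds as a conditional one about specification and efficiency. If the group main effect is the test, the attenuation to 2/3 (calcium, PTH) or 4/5 (five-visit quality-of-life scores) follows from the design for any sustained effect. If group-by-time is the test, the loss is one of power only. Against ANCOVA on the post-operative mean it ranges from 31 points (r = 0.3) to 3 points (r = 0.7) at 58 per arm, and from 37 to 14 points at 35 per arm. Against a single pre-named visit it ranges from 16 points to about none at 58 per arm, and from 16 to 3 points at 35 per arm.

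All power figures rest on an assumed 0.5 SD sustained effect, compound symmetry and complete data, and are illustrative. The ranking changes with the effect profile, which is why naming the contrast matters as much as adding the covariate. The Day 1 PTH endpoint and the sample size of 116 are outside this point.

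**What to change.** Amend Section 8.2 for calcium and PTH, and for the secondary quality-of-life and voice scores if the same model is used for them:

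- Take only post-operative visits as outcomes in a repeated-measures model with arm, visit, arm-by-visit and the pre-operative value of the same measure as covariate. Constraining the arm means to be equal at baseline is an acceptable alternative.
- Name one confirmatory contrast per measure in advance, for example the Day 12 adjusted difference or the average post-operative adjusted difference, chosen for the effect profile expected.
- Report adjusted arm differences with 95% confidence intervals at each visit (Day 12 and Month 6 for calcium and PTH).
- Describe visit as a repeated, within-patient factor.

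The cost is a change of wording in one section. No new data, visits or patients are needed.

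### Section 8.2 names a mixed-model ANOVA but makes both time and treatment between-subjects factors, and its visit list does not fit the calcium and PTH measurements

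*Combined protocol and SAP*

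**What the plan says.** Section 8.2 states that for all primary aims "data will be analyzed using a mixed model two-way analysis of variance", covering treatment group, time and interactions. It then assigns the roles. The visits are given as "Evaluation time periods (pre-surgery, Day 12, Week 6, Month 6, and 1 Year"). The same sentence goes on to say that these visits "will serve as between subjects factor and treatment group (prophylactic CND versus no CND) will serve as the between subjects factor". It promises that "Experiment-wise error will be controlled with an appropriate adjustment to the alpha-level", undertakes to check that ANOVA assumptions hold, and allows transformation or nonparametric methods where they do not.

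The primary outcome in section 2.1 is hypocalcemia. Its components include "Post-operative serum calcium (mg/dL) and PTH (pg/ml) at Day 12 and Month 6", and calcium and PTH "will be monitored post-operatively (at Day 1, Day 12, and Month 6").

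The table in section 7.1 has calcium and PTH before surgery, on Day 1, at 2 weeks and at 6 months. Its 6-week cell is blank, and its 12-month cell reads "Performed only if month 6 value is abnormal". The schedule of activities also shows no calcium or PTH at Week 6, but it marks 1 Year as 'CI'. Its procedure key defines CI as standard of care when the patient's condition warrants it, and otherwise done for research.

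Section 5.4 specifies "permuted block randomization stratified by age" and by tumor size. Section 8.2 does not mention these strata.

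**The concern.** The two sentences of section 8.2 cannot both be followed. A mixed two-way ANOVA has one repeated factor and one between-subjects factor, but here both factors are given the between-subjects role. A between-subjects time factor would mean different patients at each visit, which contradicts the visit schedule.

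This is the only quantitative model that the plan states. If the factor sentence were followed as written, with every patient-visit an independent row, the group effect and the group-by-time effect would share one error term that suits neither. The group test would reject too often and the interaction test too rarely. The promised alpha adjustment would lower the threshold but leave the error term wrong.

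Changing one word does not finish the model. For calcium and PTH, the listed times include one with no data and one whose collection rule is unclear, and they leave out Day 1.

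**Working it through.** **1. The plan's own figure.** Section 8.1 gives 116 patients (58 per arm) for 12% versus 36%, alpha 0.05 and power 0.80. The pooled-variance two-proportion formula, two-sided, gives

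n = [1.960·√(2·0.24·0.76) + 0.842·√(0.12·0.88 + 0.36·0.64)]² / 0.24² = 48.5, so 49 per arm.

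The continuity correction, (n/4)·[1 + √(1 + 4/(n·0.24))]², gives 56.5, so 57 per arm and 114 in total. That is within 2 patients of 116. The figure rests on a binary Day 1 comparison and not on the ANOVA, so this point does not touch it.

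**2. Listed times against collection of calcium and PTH.**

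| Time | Listed in 8.2 | Collected |
|---|---|---|
| Pre-surgery | yes | yes |
| Day 1 | no | yes (2.1, 7.1) |
| Day 12 | yes | yes |
| Week 6 | yes | no (7.1, schedule of activities) |
| Month 6 | yes | yes |
| 1 Year | yes | conditional on Month 6 (7.1); CI (schedule of activities) |

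Three of the five listed times match unconditional collection. The 8.2 list does match the quality-of-life rows of the 7.1 table.

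**3. Illustration of literal execution.** From the documents: 35 per arm, which is half of the lower randomization limit of 70 in section 8.1. Assumed: complete normal data with variance 1, T = 3 times (pre-surgery, Day 12, Month 6), and exchangeable within-patient correlation ρ of 0.3, 0.5 or 0.7. The documents give no ρ.

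*Group test under the null.* The true variance of an arm's mean over T times is [1 + (T − 1)ρ]/(nT). The pooled residual implies 1/(nT). The ratio is the design effect DE = 1 + 2ρ. The residual degrees of freedom are 2·3·34 = 204, so the critical t is 1.972. The true error is about 2·[1 − Φ(1.972/√DE)]:

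| ρ | DE | 1.972/√DE | True error | Simulated (20,000 runs) |
|---|---|---|---|---|
| 0.3 | 1.6 | 1.559 | 0.119 | 0.127 |
| 0.5 | 2.0 | 1.394 | 0.163 | 0.166 |
| 0.7 | 2.4 | 1.273 | 0.203 | 0.209 |

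With the correct error term, the simulated error is 0.050 to 0.053. At an assumed adjusted level of 2.5% (8.2 names no adjustment), the literal error is still 0.080, 0.112 and 0.151.

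*Group-by-time test.* Assume an arm difference of 0, 0.5 and 0.5 SD at the three times. The mean difference is 1/3, and the squared deviations sum to 1/9 + 1/36 + 1/36 = 1/6. The noncentrality is λ = n·(1/2)·(1/6)/(1 − ρ) = 35/[12(1 − ρ)], which is 4.17, 5.83 and 9.72.

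- Correct error term, noncentral F on 2 and 136 degrees of freedom: power 0.422, 0.561 and 0.794.
- Literal, simulated: 0.243, 0.193 and 0.117. The pooled residual estimates 1, while the interaction contrasts vary only by 1 − ρ, so the statistic rarely reaches the threshold.

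At 58 per arm and ρ = 0.5, simulated power falls from 0.793 to 0.419.

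**The case against.** The strongest reply is that this is a slip of one word. The term 'mixed model' already implies a repeated factor, and a sentence that gives two factors the same role reads as a drafting error. Section 8.2 also promises to check ANOVA assumptions, of which independence is one, and assigns the work to a statistician using SAS. The error rates above arise only if both safeguards are ignored. That stands, so the figures are illustration only and do not set the weight of the point. But nothing in the protocol corrects the sentence, and restoring 'within' does not settle the time levels.

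A second reply is that the mismatch in times does little harm. A Week 6 level with no data adds no observations, and Day 1 PTH below 10 pg/ml is a separate binary endpoint. That is also fair. What remains open is where the continuous Day 1 calcium and PTH values belong.

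A reader might infer three stronger conclusions that the documents do not support:

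- *That the sample size is wrong.* It does not come from this model.
- *That 1 Year calcium and PTH are drawn only after an abnormal Month 6 value.* The 7.1 table says so, but the CI key in the schedule of activities implies that they are done either way. The schedule's cell also cites a footnote 18 whose text is not in the copy available. That note may state the condition, so its absence is not counted against the plan.
- *That 1 Year must therefore be left out of the model.* If collection depended only on the recorded Month 6 value, a likelihood-based mixed model that includes Month 6 could still target the arm mean. In one check (normal data, correlation 0.5, about 16% observed), the raw 1 Year mean was biased by 0.77 SD and the model-based mean by about 0.01. With 70 patients such an estimate would be imprecise. The caution therefore applies to raw 1 Year means.

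**Conclusion.** The point holds as a specification error that should be fixed. Section 8.2 contradicts itself on the role of time, contradicts the visit schedule, and lists times that do not fit the serial calcium and PTH measures. The textual finding rests on no assumption. The numerical consequences rest on literal execution with a single pooled residual and on an assumed correlation, and they vanish once time is within-subject. They do not predict how the trial's tests will behave. Single-time endpoints and summaries, such as Day 1 PTH below 10 pg/ml and the two-week calcium total, are outside the problem.

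**What to change.** Rewrite the paragraph in section 8.2 as follows:

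- Make time the within-subject (repeated) factor and treatment group the between-subjects factor, in a mixed model clustered on patient and adjusted for the age and tumor-size randomization strata.
- List the time levels per outcome as collected. For calcium and PTH, drop Week 6 and state whether Day 1 is a level or is analysed separately.
- Reconcile the schedule of activities and its procedure key with the 7.1 table on 1 Year calcium and PTH, then decide whether 1 Year is a level. If collection is conditional, do not read raw 1 Year means as arm means.
- Name in advance the treatment contrast to be tested. Whether the pre-operative value is a covariate or a time level is a design choice for the sponsor's statistician.

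The cost is one paragraph, the reconciliation of the two tables and the matching SAS model statement. The model correction needs no new data or visits.

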Patients randomized to Arm 2 will be receive total thyroidectomy with an ipsilateral CND. The CND will be performed as described by a consensus conference of the ATA. This will include removal of the prelaryngeal nodes, the pretracheal nodes, and the paratracheal lymph nodes. The paratracheal dissection will be bounded superiorly by the cricoid cartilage and inferiorly by the innominate artery on the right and on the left by the axial plane where the innominate crosses the trachea. The superior parathyroid gland will be preserved in situ along with its primary blood supply from the superior branch of the inferior thyroid artery. The inferior parathyroid gland will be reflected laterally along with its blood supply from the inferior thyroid artery. Parathyroid autotransplantation will be performed if the glands are devascularized during dissection. Paratracheal tissue specimens will be examined for parathyroid glands that may be salvaged and transplanted before being removed from the sterile field. Suspected parathyroid glands will be confirmed by frozen section biopsy prior to autotransplantation.

Blinding: Both surgical procedures are performed through the same incision and post-operative care is identical. As such, the neck dressings are identical, allowing both the patients and study staff to be masked with regard to treatment arm randomization. Participants will remain blinded to treatment arm until the Day 12 follow-up appointment, at which point their pathology report will be reviewed with them, and unblinding will occur. Because subjective symptoms and calcium intake are two of our secondary endpoints, we will minimize participant and researcher bias in the description and treatment of post-operative symptoms in the immediate post-operative period. Because the risks of the two procedures and the post-operative instructions are identical for both arms, there is no risk associated with blinding the patients until their Day 12 follow-up. Participants who screen fail intra-operatively will be notified as to which procedure(s) was conducted immediately following surgery. The surgeon performing the procedure cannot and will not be blinded to the participant's treatment arm at any time.

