8.1. Sample size determination

At the beginning of this study, we anticipated randomizing 140 patients with clinically node negative thyroid cancer, with the goal of 116 participants completing the study. Patients will be recruited from the Endocrine Surgery and Otolaryngology Clinics at the University of Wisconsin Hospitals and Clinics. This is a high volume tertiary care center with a large thyroid practice, performing approximately 350 thyroid operations per year. Thyroid cancer accounts for 30% of thyroidectomy cases at our institution and this is the pool from which the patients will be identified (approximately 105 patients/year). Approximately 15% of thyroid cancer cases will have a positive pre-operative ultrasound, thus decreasing our pool of eligible participants to approximately 89 patients per year. With an accrual goal of 140 participants within 4 years, we would need to recruit 39% of eligible patients each year.

Permanent complications in thyroid surgery are uncommon, but these complications can be disastrous for a patient that is affected. Permanent hypoparathyroidism occurs in 1-2% of patients after a total thyroidectomy and the risk may be as high as 14% when a CND is performed. The best surrogate marker to predict an increase in permanent morbidity is the incidence of transient hypoparathyroidism, which is substantially more common than permanent hypoparathyroidism. For example, transient hypoparathyroidism occurred in 12% of our last 270 patients undergoing a total thyroidectomy. The rate of transient hypoparathyroidism in patients treated with a CND has been shown in the literature to be significantly higher. The rate of transient hypoparathyroidism in recent large retrospective studies was reported to be between 38-51%.

We assumed a power of 0.8 and an alpha of 0.05. For sample size calculations we made the assumption that the incidence of transient hypoparathyroidism after a total thyroidectomy alone is 12% and that an increase to 36% (or tripling of the risk) is clinically significant. The rate of hypoparathyroidism in Arm 1 is based upon our last 270 patients and is a reliable estimate. The incidence in the CND arm is based on a

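### The plan lists six unordered primary endpoints, sizes one at an unadjusted 0.05 and promises an undefined alpha adjustment, so the 80% power at 116 patients depends on a testing rule it does not state

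*Combined protocol and SAP*

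**What the plan says.** **Section 2.1 (primary outcome and endpoints)** has six bullets under one objective, the rate of transient and permanent hypocalcemia:

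1. Day 1 PTH below 10 pg/ml
2. Serum calcium and PTH at Day 12 and Month 6
3. Total calcium intake over two weeks
4. Symptom frequency: "Hypocalcemia symptoms in first 2 weeks (average episodes/day"
5. Symptom severity
6. Need for calcium and calcitriol at Month 6

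No order or hierarchy is given.

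**Section 3 (Blinding)** labels some of these differently: "subjective symptoms and calcium intake are two of our secondary endpoints".

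**Section 8.1** sizes the trial on the first bullet only. Its error rates are: "We assumed a power of 0.8 and an alpha of 0.05". It assumes that the incidence "after a total thyroidectomy alone is 12% and that an increase to 36% (or tripling of the risk) is clinically significant", and concludes: "With these assumptions the sample size is 116, with 58 patients per arm". It refers to one primary endpoint: "Due to the short follow up for our primary endpoint (post-operative day 1". The same section, and Section 12.7, also mention a primary recurrence endpoint, although Section 2.2 places recurrence among the secondary outcomes.

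**Section 8.2** opens with all primary aims, prescribes a mixed-model analysis of variance, and adds: "Experiment-wise error will be controlled with an appropriate adjustment to the alpha-level". The method, the number of tests and the set of tests covered are not given. The time points listed for that model do not include Day 1.

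**The concern.** The sample size and the multiplicity promise were written separately. Section 8.1 spends the whole 0.05 on one endpoint. Section 8.2 says that alpha will be adjusted in an analysis covering every primary aim, and Section 2.1 supplies at least six candidates for that adjustment.

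Two things are at stake. The first is power: if the adjustment reaches the Day 1 comparison, 58 per arm was calculated at a larger alpha than the one that will be used. The second is interpretation: the hypothesis in Section 1.2 is a higher complication rate, and nothing says which of the six results decides it. Section 8.1 also reports that preliminary data have been examined and that subjective data will be brought into every primary and secondary outcome measure. A primary family left open at that stage is harder to defend later.

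Dropping the adjustment while keeping all six as primary is no way out. Six independent tests at 0.05 would give a chance of at least one false positive of 1 − 0.95^6 = 26.5%; positively correlated endpoints would give less.

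**Working it through.** **Inputs from Section 8.1:** p1 = 0.12, p2 = 0.36, alpha 0.05, power 0.80, 58 per arm. **Assumed, because not stated:** a two-sided test, and Bonferroni as the example adjustment.

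**Step 1: reproduce the plan's figure.** With mean proportion 0.24 and difference d = 0.24:

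- n = [z(α/2)·√(2·0.24·0.76) + z(0.80)·√(0.12·0.88 + 0.36·0.64)]² / d²
- n = (1.960·0.6040 + 0.8416·0.5797)² / 0.0576 = (1.1838 + 0.4879)² / 0.0576 = 48.5
- With continuity correction: n/4·[1 + √(1 + 4/(n·d))]² = 56.5, so 57 per arm and 114 in total

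This is within two patients of the stated 116. The other variants tried fall well short: 98 without correction, 94 by arcsine, 92 unpooled, and 78 or 94 one-sided. The stated size therefore matches a two-sided, continuity-corrected calculation at the full 0.05, with no allowance for multiplicity.

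**Step 2: power for the Day 1 endpoint when alpha is split over m tests.** For each pair of event counts, take the product of the two binomial probabilities, and sum over all pairs with p ≤ 0.05/m.

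| m | alpha | 58 per arm: Fisher / chi-square | 70 per arm: Fisher / chi-square |
|---|---|---|---|
| 1 | 0.0500 | 83.0% / 88.0% | 89.7% / 93.1% |
| 2 | 0.0250 | 74.2% / 80.5% | 83.4% / 88.0% |
| 3 | 0.0167 | 69.4% / 76.1% | 80.0% / 84.7% |
| 6 | 0.0083 | 60.2% / 67.5% | 72.3% / 78.1% |

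Normal approximations at 58 per arm agree: 87% (pooled) and 81% (continuity-corrected) for m = 1, and 66% and 57% for m = 6.

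**Step 3: which m applies.** The plan does not fix it.

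- Six bullets give m = 6.
- Following Section 3 and setting aside calcium intake, symptom frequency and symptom severity leaves three bullets, m = 3.
- The second bullet holds four measures (calcium and PTH, each at two visits). Counting them separately gives 6 + 3 = 9 tests, with power of 54.1% / 61.9% at 58 per arm.
- The single primary endpoint named in Section 8.1 gives m = 1.

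**Step 4: size needed for 80% at the adjusted alpha.** The Step 1 formula with z at 0.05/(2m) gives 134 in total for m = 2, 148 for m = 3 and 168 for m = 6. For m = 6: (1.5935 + 0.4879)² / 0.0576 = 75.2, corrected to 83.3, so 84 per arm.

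**Step 5: the lower recruitment bound.** At 35 per arm (70 randomized, Section 8.1), power is 56.8% / 66.5% with no adjustment at all. That shortfall comes from the reduced target and is a separate issue.

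**The case against.** The strongest defence is that the statements can be reconciled. Section 8.1 names one primary endpoint. If Day 1 hypoparathyroidism is tested first at 0.05 and only later tests are adjusted, then the alpha in 8.1, the single endpoint in 8.1 and the adjustment in 8.2 all hold, and 116 patients give 83.0% to 88.0%. The adjustment sentence also sits in a paragraph about a mixed model whose time points leave out Day 1, so it can be read as covering comparisons within that model. Bonferroni is the severe case: under Holm, power would lie between the adjusted and unadjusted values. The divisor of six is not firm either.

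All of this stands as a limit on what can be claimed. A reader might infer that the 80% power is simply not delivered, or that the sections cannot all be true. The documents support neither, because a fixed sequence would rescue the power.

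What does not stand is the idea that the plan already contains that rule. No section gives a testing order or exempts Day 1 from the adjustment, and 8.2 opens with all primary aims. The conflict between the labels in Sections 2.1 and 3 also remains under any testing rule.

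**Conclusion.** The point holds as a conditional one. The primary family is labelled inconsistently, the multiplicity rule is undefined, and the sample size makes no allowance for it.

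At 116 patients, a test at the full 0.05 meets the stated 80%. Under Fisher's test any Bonferroni split misses it; under the uncorrected chi-square test a two-way split only just keeps it (80.5%). With six tests, power is 60.2% to 67.5%, which is 12.5 to 19.8 points below 80%. If all 140 are analysed, three tests reach 80.0% to 84.7%, but six do not (72.3% to 78.1%).

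These figures rest on 12% versus 36%, equal arms, two-sided tests, no loss and Bonferroni. A reader might attribute the low power at 70 patients to multiplicity, but most of that gap is present before any adjustment.

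**What to change.** - Name Day 1 PTH below 10 pg/ml as the single primary endpoint, tested at two-sided 0.05, and state in Section 8.2 which test is used for it.
- Make the other Section 2.1 measures secondary, either with Holm adjustment over a listed family or with estimates and confidence intervals only.
- Align Sections 2.1, 3 and 8.2, and settle the recurrence label in Sections 2.2, 8.1 and 12.7.
- Date the change, and make it before any comparison by arm.

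This agrees with the single endpoint in Section 8.1 and the secondary label in Section 3, and it needs no patients beyond the 116. It is not free: the objective covers transient and permanent hypocalcemia, and the Month 6 measures would lose confirmatory primary status. Section 8.1 argues that the transient rate is the best surrogate for permanent morbidity, which may justify the choice, but the sponsor must make it openly.

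If several endpoints stay primary, list them, name the method, and restate the power at the adjusted alpha. By the formula that matches the plan's own figure, 80% for the Day 1 endpoint needs 148 patients with three tests and 168 with six, both above the current maximum of 140.
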